5 STUDY POPULATION

5.1 INCLUSION CRITERIA

To be eligible for the focus group (Aim1):

- being a Queens WTCHP responder who agreed to be contacted to participate in research,
- having PTSD as per DSM criteria as indicated by the WTC General Responder Data Center (GRDC),
- having elevated PTSD symptoms, as per a PCL-S⁸⁵ score ≥ 44 during an annual monitoring visit between 2018-2020.

To be eligible for randomized pilot (Aim 2):

- being a WTCHP responder who agreed to be contacted to participate in research
- having PTSD as per DSM criteria indicated by the GRDC
- having elevated PTSD symptoms, indicated by a PCL-S⁹³ score ≥ 44 during an annual monitoring visit between 2018-2020
- having a score of 33 or greater on the PCL-5⁹⁴ delivered during the initial phone screen to determine current symptomatology
- meeting diagnostic indication of PTSD using a Clinician-Administered PTSD Scale (CAPS), which is a clinical interview assessment.⁹⁵

5.2 EXCLUSION CRITERIA

Exclusion criteria for the focus group (Aim1):

- being physically or mentally unable to consent/participate,
- inability to speak, read, or write in English

Exclusion criteria for randomized trial (Aim 2):

- being physically/mentally unable to consent and participate
- inability to speak, read, or write in English,

Protocol Number: 21-0640

February 1, 2022

- exhibiting any current psychotic or manic symptoms or active substance dependence, as per the standard MINI neuropsychological assessment.⁹⁶, or current suicidal or homicidal intent/plan, as per the Columbia-Suicide Severity Rating Scale (C-SSRS)¹⁰⁴
- active disease involving the auricle or ear canal (e.g., otitis media, tinnitus, infection, perforated tympanic membrane, vestibular and/or balance, excessive cerumen production, skin irritation), unwilling to remove a piercing (e.g., daith or tragus), or use a device (e.g., hearing aid, cochlear implant) that would preclude daily use of the earpiece.
- history of unilateral or bilateral vagotomy.
- Current pregnancy (self-report)
- previously implanted electrically active medical devices (e.g., cardiac pacemakers, automatic implantable cardioverter-defibrillators, VNS).
- other major conditions, that in the judgment of the investigators/WTCHP medical staff, would make the participant unsuitable for inclusion or would interfere with the participant participating in or completing the study. these include:
 - current treatment with psychotropic medication, including tricyclics, antipsychotics, mood stabilizers, bupropion, barbiturates, stimulants, antiepileptics, opioid medications.
 - current diagnosis or history of any clinically significant cardiac, endocrinologic, pulmonary, neurologic, psychiatric, hepatic, renal, hematologic, neurologic, gastrointestinal, or immunologic.
 - history of any of the following cardiovascular conditions: Moderate to severe congestive heart failure (New York Heart Association class III or IV); Recent (within past 6 months) cerebrovascular accident, myocardial infarction, coronary stenting; Uncontrolled hypertension as defined by a confirmed systolic blood pressure > 160 mmHg or diastolic blood pressure > 100 mmHg.
 - history of or active seizure disorder.
 - history of recurrent vasovagal syncope episodes.
 - diagnosis of cancer (other than non-invasive skin cancer or carcinoma in-situ of the cervix) within the 5 years prior to study entry.
 - history of concurrent illness that requires hospitalization within 30 days prior to study entry
 - have hypertension/hypotension uncontrolled by medication
 - participation in another investigational trial during the 30 days prior to study entry or during this project

5.3 LIFESTYLE CONSIDERATIONS

During this study, participants are asked to:

- Abstain from eating or drinking (besides water) for at least 3 hours prior to each visit
- Abstain from alcohol for at least 8 hours prior to each visit
- Abstain from tobacco and nicotine products for at least 1 week prior to each visit
- Abstain from recreational drugs for at least 1 week prior to each visit
- Abstain from exercise for at least 8 hours prior to each visit

Protocol Number: 21-0640

February 1, 2022

- Women of childbearing potential should use birth control for the entire duration of the study. Double-barrier methods (condoms with spermicide, sponge with spermicide, or diaphragm with spermicide) or not having sex may be used.

5.4 SCREEN FAILURES

Screen failures are defined as participants who screened as potential participants in the clinical trial, but do not complete the first study visit or consent because they did not qualify based on their CAPS scored and become deemed ineligible.

5.5 STRATEGIES FOR RECRUITMENT AND RETENTION

Recruitment (Aim1):

The GRDC will provide a list of all Queens WTCHP responders who meet eligibility criteria, and their corresponding contact information, to the study team. A Collaboration Request Letter was granted by the GRDC to provide this information, and will be executed upon Notice of Award. From this list, a random sample of 10 responders will be contacted by phone, email, and/or mail for focus group recruitment. After 10 responders have consented, the focus group will be scheduled and conducted at the Queens WTCHP. Due to potential COVID-19 restrictions the focus group can be done remotely if necessary.

In order to maximize recruitment, mailings will be sent to all eligible Queens WTCHP responders (N=477) and the focus group will be advertised within the Queens WTCHP.

Recruitment (Aim 2):

As per the GRDC, there are currently 477 Queens WTCHP responders who consented to be contacted to participate in research with a PCL-S score ≥ 44 since 2018, and who met DSM criteria for PTSD. From that list of 477, 30 responders will be recruited over the course of 10 months as follows: First, the list of responders that meet initial eligibility requirements will be randomly ordered. Next, the coordinator will contact responders from this list in sequential order by phone, in which the PCL-5 will be administered to confirm current probable PTSD (score ≥ 33), so that the likelihood of bringing someone in for a diagnostic interview who does not currently meet criteria for PTSD is minimized. Then the coordinator will discuss participation in the CAPS interview, to determine further eligibility for the study. If the responder agrees to come in for a CAPS assessment, [name] or [name], [name] or [name] will conduct a CAPS assessment and the standard MINI to assess for psychiatric exclusion. For the suicidality portion specifically, we will utilize the Columbia-Suicide Severity Rating Scale (C-SSRS). [name], [name] and [name] will be trained and supervised on CAPS by [name]. If the CAPS is indicative of a current diagnosis of PTSD and exclusion criteria are not met, [name] or [name] will then come to the fitting appointment to consent and enroll the responder into the study if they continue to express interest. The consent form will be mailed or given ahead of time to review.

The responder will receive \$20 and transportation costs, \$25, for completion of the CAPS regardless of whether or not he or she is eligible for the pilot study. Based on our previous research,⁹⁷ we expect that of the 477 potential participants, approximately 182 will need to be called in order to reach a 33% screening participation rate, to yield 60 responders who meet the phone screen criteria and agree to come in for the CAPS interview. Of those 60 responders, we expect that 66% (n=40) will meet criteria for PTSD as per the CAPS, and will therefore be eligible for the study based on [name] previous study involving recruitment and enrollment of military Veterans with PTSD.⁹⁸ Based on our prior experience of clinical taVNS studies on both healthy and disease cohorts,³⁷ of those 40, we expect that at least 75% (n=30) will agree to continue with study participation.

In order to increase recruitment, we are working with Mount Sinai WTCHP Data Center to identify additional eligible patients. These participants previously consented to be contacted for research.

This information includes: names, contact information (mailing address, phone numbers and email addresses) for members who scored ≥ 44 on their most recently completed PCL/PTSD checklist since 1/1/2019 who live within a 10 mile radius from the Feinstein Institutes for Medical Research ([name]).

This will be provided to us from Mount Sinai WTCHP Data Center, we will not be giving any information to them.

Even though we have a data use agreement in place, we are requesting a HIPAA waiver of authorization to receive and possess the WTCHP PHI. Providers previously gave permission to be contacted, but in order for us to only reach out to those potentially eligible, we need to know additional information and it isn't feasible to reach out to each participant for this information. All participants are consented prior to any research activity.

5.6 COSTS

There are no foreseeable costs that participants may incur through participation in this research study, other than costs of travel which will be reimbursed with a flat fee per study visit. No research procedures will be billed to insurance and all clinical laboratory tests conducted for this study will be paid for by the study.

5.7 COMPENSATION

Compensation (Aim1):

Protocol Number: 21-0640

February 1, 2022

Participants will be compensated \$25 for their participation in the focus group as well as a flat reimbursement for travel/mileage of \$25 per participant.

Compensation (Aim 2):

CAPS Interviews: Incentives of \$20 per participant as well as a flat reimbursement for travel/mileage of \$25 per participant

taVNS Fitting: Incentives of \$25 per participant as well as a flat reimbursement for travel/mileage of \$25 per participant

Baseline Measurement: Incentives of \$30 per participant, as well as a flat reimbursement for travel/mileage of \$25 per participant

Follow-Up Measurement: Incentives of \$35 per participant as well as a flat reimbursement for travel/mileage of \$25 per participant

Greenphire ClinCards: **Greenphire ClinCards** will be used for reimbursement per institutional policy. Each participant will receive a new ClinCard at each study visit.

Amazon electronic gift cards will also be utilized for reimbursement for ease with participants

Study Incentives

Time point	Incentive	Travel	Total
Focus Group	\$25	\$25	\$50
*CAPS Interview	\$20	\$25	\$45
taVNS Fitting	\$25	\$25	\$50
Baseline	\$30	\$25	\$55
Follow-up	\$35	\$25	\$60

* The responder will receive \$20 and transportation costs, \$25, for completion of the CAPS regardless of whether or not he or she is eligible for the pilot study. If not eligible the responder would not take part in any additional portion of the study.

Protocol Number: 21-0640

February 1, 2022

** If focus group or CAPS interview are done remote, reimbursement for the transportation will not be given.

5.8 RESEARCH INJURY COMPENSATION

If participants are injured from study participation, s/he will be provided treatment by Northwell Health. However, s/he or their insurance company will be responsible for the associated costs. No money will be given to participants.

6 STUDY INTERVENTION

6.1 STUDY INTERVENTION(S) ADMINISTRATION

6.1.1 STUDY INTERVENTION DESCRIPTION

Aim 1: A Focus Group Discussion Guide will be finalized by the research team prior to recruitment (see Appendix 1 for example blank focus group data collection instrument). It will include questions to understand the relevance, feasibility and acceptability of: (1) using a taVNS device generally, (2) using it as treatment for PTSD, (3) the implementation protocol of the device, (4) the pilot study protocol (including the methodology details, timing, and both self-report, clinical, and biological assessments), and (5) the appropriateness of outcome measures. The estimated duration for the focus group is \approx 90 minutes. Drs. [name] and [name] will co-lead the focus group and the coordinator will take notes, write the minutes, and audio-record the session. [name] and/or [name] will demonstrate the device. Individuals will have the opportunity to handle the devices and there will be sanitizing wipes to be used in between. The focus group will be transcribed for qualitative analyses.

Aim 2:

Table 1. Aim 2 Outcome Measures	
Primary Outcome Measures (measured at 8 weeks)	
FEASIBILITY	
Recruitment	
-% responders who meet criteria 1-3 who accepted to come in for the CAPS interview (goal=33%)	
-% eligible responders who meet criteria 1-4 of those who came in for the CAPS interview (goal=66%)	
-% eligible responders who meet all criteria and were recruited and consented (goal = 75%)	
Retention	
-% participants who complete baseline and 8-wk measures (both survey and biological measures) (goal = 90%)	
Adherence	
-% participants who used taVNS 15 min/day once a day for 8 weeks (21 hours total) (goal=80%)	
Secondary Outcome Measures (measured at 8 weeks)	
ACCEPTABILITY	
Collection of Measures	
-Time (minutes) to fill out questionnaires (goal =<30 min)	
-Missing data from questionnaires: % items complete on the baseline and 8-wk self-report surveys (goal=90%)	
-Time (minutes) to collect biological data and blood draw (goal=10 min at baseline and 10 minutes at follow-up)	
-Rate of refusal of biologic measurements/blood draw (goal=5% refusal)	
Satisfaction	
-taVNS Intervention Study satisfaction survey (Adapted from Bakken et al.) (range=12-60; goal=100%-with score >47 among intervention group) ¹⁰⁰	
Tertiary Outcome Measures (measured at baseline and 8 week follow-up)	
Mental health symptoms (assessed to indicate signals for hypothesis generation)	
-PTSD diagnosis and severity: CAPS interview ⁹⁵ (measured at screening and 8 week follow-up); PTSD Diagnosis: Yes/No; PTSD Severity score range=0-80)	
-PTSD symptom score (PCL-5 ⁹⁴ , range=0-80)	
-Anxiety symptom score (GAD-7 ¹⁰¹ , range=0-21)	
-Depression symptom score (PHQ-9 ¹⁰² , range=0-27)	
-Sleep score (Pittsburg Sleep Quality Index ¹⁰³ , range=0-21)	
Biologic Measures (assessed to indicate signals for hypothesis generation regarding potential mechanisms of action) At baseline, these will be measured 10 min before, during and 10 min after the initial taVNS administration	
-Heart rate/HRV (6-lead ECG, DI Powerlab) (beats/min, range=40-150)	
-EEG(DSI-24) (band-power dB changes, range=0-10)	
-Pupil Dilation (Tobii Pro Glasses 2) (pupil diameter in mm, range=2-8mm)	
-Galvanic Skin Response (GSR electrodes, ADI Powerlab) (skin conductance in microSiemens, range=0-50mS)	
-Skin Temperature (Thermistor Pod, ADI Powerlab) (Celcius, range=30-35C)	
-Respiratory Rate (Respiratory Belt, ADI Powerlab) (breaths per minute, range=3-20BPM)	
-Beat-to-Beat Blood Pressure (Human Non-Invasive Blood Pressure Nano Interface, ADI Powerlab) (mmHg, range=50-150mmHg)	
-Inflammatory Markers (blood draws at baseline before and after initial taVNS and at 6 week follow-up: TNFa, IL-1 β , IL-6, IL-10, IL-12, IL-17, CRP, Cortisol, Alpha Amylase)	
-Facial & Neck Electromyography (EMG electrodes, ADI Powerlab) (millivolts, range=0-15mV)	

Procedure: After each of the 30 responders are enrolled (3 per month), they will be scheduled within that same month for an appointment at FIMR to be fitted with a custom-made taVNS device, a wearable TENS unit called the Nesos System. They will be compensated for their time/transportation. We expect to have approximately 1 visit per month for fittings, so that all 30 participants will be enrolled and fitted over 10 months. Participant visits will be staggered in order to protect privacy. After the devices are customized and delivered to FIMR (within approximately 1 month), responders will be called to FIMR for a baseline visit. One of the researchers from the Feinstein Institutes will assess the fit of the device and calibrate the level needed for each responder. At the baseline visit, responders will be given the device that matches their randomization sequence ID number. Each responder will also be given, along with the taVNS device, a locked-down Android Nexus 5X or Pixel phone to interface with the device and record the usage data. Responders will then be given a self-report survey to complete that asks demographic information, MH treatment-related information, and validated measures of MH and sleep (Table 1). Appendix 1 contains blank, sample self-report/interview measures. A research nurse will also collect 12 mL of blood to assess baseline and follow-up levels of inflammatory markers including Tumour Necrosis Factor alpha (TNF α), Interleukin (IL)-1 β , IL-6, IL-10, IL-12, IL-17, C Reactive Protein (CRP), cortisol, and alpha amylase. During the baseline visit, responders will also be shown how to use the device by Drs. [name] or [name]. The responders will use the device for one 15-minute session under the supervision of Drs. [name] or [name]. Biological non-invasive measures (not blood draw) of autonomic nervous system function and balance, as detailed in prior studies from the our group⁸⁰ and others, will be assessed 10 minutes before using the taVNS device. (see Table 1).

These non-invasive biological measures include: Respiratory belt, ECG, GSR, NIBP, EEG, Eye tracking.

Protocol Number: 21-0640

February 1, 2022

The first sensor to be attached to the participant is a respiratory belt that goes around the torso. It is tightened without discomfort such that breathing causes the belt to stretch, which provides inspiration (inhalation) and expiration (exhalation) times to infer respiration rate. Next, the 6-lead electrocardiography (ECG) will be recorded from wires connected from a bio-amplifier, which gathers and increases physiologic signals, to four foam electrodes that are adhesively attached to the left shoulder, the right shoulder, the left ankle, and the right ankle. The right ankle provides a ground, while the remaining three leads provide recordings of the electrical potentials between different sites that represent the electrical activity of the heart in real-time.

Additional sensors are placed on the wrist and hands of the participant. The first set records galvanic skin response (GSR) by attaching two dry, metal electrodes with Velcro attachments on two fingers, preferably the pointer and ring fingers on the dominant hand. These electrodes measure the changes in skin conductance that can reflect changes in sweat gland activity. A wrist device will be placed to record non-invasive blood pressure (NIBP) from the middle finger on the participant's non-dominant hand. The wrist device is placed with a Velcro strap on the wrist, while a small cuff is placed on the middle finger. The wrist device provides air and power for the cuff to inflate and deflate to measure changes in blood pressure. A dry electrode electroencephalography (EEG) cap will be placed on the head of the participant. This cap offers low noise and high signal quality of non-invasive brain recordings without an uncomfortable cap that may require conductive gels. This cap can be placed on the head of the participant and record comfortably through hair without any gel. The final device to be placed on the participant is the eye tracking glasses. These are easily wearable and mobile glasses with multiple small cameras to track gaze and pupil size. If the participant wears prescription glasses, these will be removed and replaced with the eye tracking glasses (with the appropriate prescription lenses) for this study."

Responders will then be instructed to use the device once a day, every day at home, for 15 minutes intervals over 8 weeks. The devices have a safety feature where they cannot be used for more than the intended timepoints daily and the stimulation parameter will be set by the investigator and cannot be altered by the participant. The date and time stamp of each use will be recorded on the application. The application only assesses usage/compliance and has no ability to capture any personal or other information. All phones containing the Nesos application is collected at the end of the study. Responders are requested to come in 8 weeks post-baseline and the same measures will be recorded again (self-report, biological and blood draw; see Table 1).

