9.3 STATISTICAL ANALYSES

9.3.1 ANALYSIS OF THE EFFICACY ENDPOINTS

Protocol Number: 21-0640

February 1, 2022

Planned Data Analysis. The purpose of the pilot study is to determine whether an RCT evaluating the efficacy of taVNS on mental health outcomes is feasible, acceptable, and satisfactory for WTC responders with PTSD. The total sample size for the Aim 2 pilot trial is 30 World Trade Center Health Program responders with PTSD. Primary endpoints are based on feasibility. Specifically, recruitment, retention, and adherence, will be measured. Recruitment is defined as the percent of eligible responders who meet all study criteria and were recruited and consented to be in the study. Retention is defined as the percent of participants who completed both baseline and 6-week measures. Adherence is defined as the percent of participants who used taVNS 15 minutes a day once a day for 8 weeks. Secondary endpoints of acceptability include participant satisfaction and ability to complete the various mental health, blood draw and biologic measures with limited refusal, limited non-response, and within acceptable amounts of time. Tertiary endpoints include mental health and biologic measures. Please see the outcomes measures section for detailed definitions.

All measures will be described using frequency/percent or mean (SD) as appropriate, overall and by taVNS and sham group, with corresponding 95% confidence intervals to interpret the precision of the estimates. Median and interquartile range may also be used if discrete data are skewed. For the tertiary outcomes measuring mental health and biologic data, descriptive statistics for each time point, as well as differences over time (baseline to 8 week follow-up), will be calculated. Differences in biologic (non-inflammatory) outcomes only will be assessed from the first time point at baseline and the last time point at 8 weeks for long-term effects. Within-subject correlation of acute and long-term measures will be reported. Estimates and variances at each time point will be used to generate hypotheses and calculate effect sizes for a larger future RCT. Since effect sizes observed in pilot studies are crude, due to the small sample size, they may not be indicative of the true difference in the larger population and will be interpreted with caution.

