will not be utilized while the study is in progress. The only data collected are session metrics for evaluating usage compliance (user is intended to perform 1-2 15-minute sessions/day for 8 weeks). The phone is equipped with a Data-only SIM (no phone or SMS capabilities). This provides an Internet connection for the phone. Upon completion of treatment session, session metrics are transmitted from the application to the Nesos Google Firestore database. This information is transmitted securely through an SSL connection. The application has write-only access to record treatment session metrics. Stored data is backed-up and replicated in a Google BigQuery database. This is done via a Google cloud function triggered by new data arriving in Firestore. The BigQuery database is accessible as a data source for Nesos's customized Google DataStudio dashboard. Data stored at rest is encrypted (<https://cloud.google.com/security/encryption-at-rest/>), and protected by Google's infrastructure. Data stores are only available to Nesos's internal cloud administrator. The Nesos dashboard is the only other means of accessing data. The dashboard is customized to display usage compliance data for each of the site's subjects. The dashboard cannot be used to modify any data, nor does it have any data-write access. No subject information is available nor stored. The dashboard is restricted in access and view-only for the research team. Authentication is via a Google account that has been granted access to the dashboard. Both the Firestore and BigQuery databases are secured to prevent unauthenticated access. The Nesos application on the phone is not generally available (i.e. not in app store), and all phones containing the Nesos application are collected at the end of the study. Participants will be asked to return all items at their last visit. In the event they left something at home they will be provided with a prepaid label for return.

Data Management Plan

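### The primary adherence outcome totals once-daily use over 8 weeks as 21 hours when it is 14, and sections disagree on the intended sessions per day

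*Protocol*

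**What the plan says.** Adherence is one of the primary feasibility measures (Protocol sections 1.1, 3 and 8.1). The protocol describes the schedule behind it in six places.

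- Section 6.1.1, Table 1 (primary outcomes): "participants who used taVNS 15 min/day once a day for 8 weeks (21 hours total) (goal=80"%).
- Section 6.1.1, Procedure: participants are "instructed to use the device once a day, every day at home, for 15 minutes intervals over 8 weeks". The same paragraph describes a safety feature of the devices: "they cannot be used for more than the intended timepoints daily".
- Section 9.3.1: "Adherence is defined as the percent of participants who used taVNS 15 minutes a day once a day for 8 weeks". No hour total is given.
- Section 10.1.6, under the heading on measuring and reporting adherence: the app collects "session metrics for evaluating usage compliance (user is intended to perform 1-2 15-minute sessions/day for 8 weeks").
- Section 10.1.6, Data Management Plan, and section 10.1.8.1: the same app metrics are described with an intended two 15-minute sessions per day for eight weeks.

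Two places still carry a 6-week time point. Section 9.3.1 states: "Retention is defined as the percent of participants who completed both baseline and 6-week measures". Table 1 lists inflammatory markers from "blood draws at baseline before and after initial taVNS and at 6 week follow-up". The retention row of Table 1 says 8 weeks.

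On thresholds, sections 1.1, 3 and 8.1 define feasibility as 70% for adherence and 70% for retention. Table 1 sets goals of 80% and 90%, and sections 8.1 and 9.1 give those same figures as expected values. Recruitment is 75% throughout.

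**The concern.** The hour total contradicts the schedule in its own row of the primary outcome table. An analyst who scores cumulative app time against 21 hours would class every fully compliant once-daily user as non-adherent.

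The session-count conflict is a second problem. The device limits daily use to the intended number of sessions, so someone has to set that limit, and the protocol supports either one or two. The sections that describe the compliance data point to one to two, or two, while participants are told one. Read against two a day, a perfect once-daily user appears to have done half of what was asked. The lower confidence limit for adherence is meant to inform planning of the future RCT, so a misread rate would carry forward.

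A lesser point concerns the bar itself: no sentence says how the 70% criterion relates to the 80% and 90% goals.

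**Working it through.** **Inputs.** 15 minutes per session, once a day, 8 weeks = 56 days, stated total 21 h (Table 1). One supervised session at the baseline visit (section 6.1.1, Procedure: "The responders will use the device for one 15-minute session under the supervision of" a study investigator). Alternative frequency of two a day (sections 10.1.6 and 10.1.8.1). Alternative duration of 6 weeks = 42 days (section 9.3.1 and the blood-draw row of Table 1). Sample size 30.

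**Formula.** Total hours = days × sessions per day × 15 / 60.

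**Attempt to reproduce 21 h.**

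| Schedule | Calculation | Hours |
|---|---|---|
| 8 weeks, once a day (as defined) | 56 × 1 × 15 / 60 | 14.0 |
| 8 weeks, once a day, plus supervised session | 57 × 15 / 60 | 14.25 |
| 8 weeks, twice a day | 56 × 2 × 15 / 60 | 28.0 |
| 6 weeks, once a day | 42 × 1 × 15 / 60 | 10.5 |
| 6 weeks, twice a day | 42 × 2 × 15 / 60 | 21.0 |
| 8 weeks, 1.5 a day | 56 × 1.5 × 15 / 60 | 21.0 |

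The defined schedule does not give 21 h. Neither does any whole number of sessions per day over 8 weeks.

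**Size of the discrepancy.** 21 h is 21 × 60 / 15 = 84 sessions. The definition gives 56. The excess is 28 sessions, or 7 h, which is 7 / 14 = 50% above the correct total. At 15 minutes once a day, 84 sessions would take 84 days, or 12 weeks.

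**Consequence if the figure or the other schedule were applied.** A perfect once-daily user reaches 14 / 21 = 67% of the stated total. With the daily limit set to one session, the most anyone can log is 14.25 h, so 0 of 30 could reach 21 h. Against two a day, the same user reaches 14 / 28 = 50%.

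**Thresholds with 30 participants.** 70% is 21 people, 80% is 24 and 90% is 27. An adherence count of 21, 22 or 23 (70.0%, 73.3%, 76.7%) meets 70% and misses 80%. A retention count of 21 to 26 (70.0% to 86.7%) meets 70% and misses 90%.

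**The case against.** The strongest reply concerns weight. The operative rule is once a day for 8 weeks, and the 21 hours is only a parenthesis after it. Section 9.3.1 repeats the rule without any hour total, participants get the same instruction, and no sentence says that adherence is scored by comparing cumulative hours with 21. Every use carries a date and time stamp, so the rule can be applied directly. This stands: the zero-of-30 result is conditional on a literal use of the total, and the data remain usable. It does not remove a wrong figure from a primary outcome definition.

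It can also be said that the daily limit is described directly after the once-daily instruction, so its meaning there is clear, and that the other sections mention session counts in passing while describing data storage. That is fair for the Data Management Plan and section 10.1.8.1. It is weaker for the part of section 10.1.6 headed as adherence measurement, where one to two sessions is given as the intended use.

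The origin of the 21 hours cannot be settled. Two sessions a day for 6 weeks fits, and 6-week wording survives elsewhere. So does 1.5 sessions a day over 8 weeks, the midpoint of one to two. Either is inference, and the error does not depend on it.

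On the thresholds, a success criterion below the expected rate is ordinary in a pilot, so 70% and 80% or 90% can coexist. But section 8.1 cites Table 1 immediately after the 70% figure, and Table 1 shows different numbers. A clarifying sentence is still needed.

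**Conclusion.** The protocol is wrong as written on two counts. The hour total in the primary adherence outcome is 21 where its own definition gives 14 (84 against 56 sessions). The intended daily number of sessions is stated as one, as one to two, and as two. The first follows from the protocol's own figures without any outside assumption. The second is a direct contradiction between sections, affecting both the device setting and the standard against which compliance data are read.

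The practical harm depends on which text is followed: none if the once-daily rule is applied to the time-stamped sessions, and complete misclassification of compliant users if 21 h is used as the threshold. Because the once-daily wording agrees in Table 1, the participant instruction and section 9.3.1, it is most likely what was intended. That is a judgement for the investigators to confirm. The 70% versus 80% and 90% question is a clarification and does not drive this conclusion.

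**What to change.** 1. In Table 1, change 21 hours to 14 hours.
2. In section 10.1.6 (both the adherence-measurement text and the Data Management Plan) and in section 10.1.8.1, state one 15-minute session per day. If twice daily is in fact intended, change Table 1, the Procedure text in section 6.1.1 and section 9.3.1 instead, and use 28 hours.
3. In the same edit, check the 6-week wording in the retention definition of section 9.3.1 and in the blood-draw row of Table 1 against the 8-week follow-up.
4. Add one sentence stating that 70% is the feasibility criterion for adherence and retention and that 80% and 90% are targets or expected values, or use one figure for each throughout.

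The last item should be settled before anyone looks at adherence. Section 10.1.6 says app data will not be used while the study is in progress, but it also schedules adherence review every 5 participants or at bi-monthly meetings and gives the research team a view-only usage dashboard. The safe deadline is therefore before the first such review, and in any case before usage data are extracted.

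The cost is wording only. No visits, data or participants are added, the app already logs each session, and the precision figures in Table 2 do not change.
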